## Acronyms and Abbreviations

CPAP = Continuous Positive Airway Pressure  
bCPAP = Bubble Continuous Positive Airway Pressure  
EFS = Early feasibility study  
HCW= Healthcare worker  
RSS = Silverman Anderson Respiratory Severity Score[1]  
WHO = World Health Organization

## Operational definitions

PATH bCPAP kit without blenders	bCPAP (tubing/ cannula/ bubbler) without blenders
PATH bCPAP kit with oxygen blenders	bCPAP (tubing/ cannula/ bubbler) with blenders
PATH blenders	only the PATH blenders

Kiwoko bCPAP refers to the pre-existing bCPAP that has been in place at Kiwoko hospital since 2012. It is assembled from spare parts and donated nasal cannulas.(12)

## Abstract

Preterm birth is responsible for 1/3 of deaths under age five- the majority which occur in resource-constrained settings. Many of these deaths are due to respiratory failure which can be treated with bubble continuous positive airway pressure (bCPAP). Commercialized bCPAP devices are expensive, leading resource-constrained settings to make and use improvised devices. These improvised devices have not been tested for performance and run on 100% oxygen. WHO guidelines strongly advise against the use of 100% oxygen—particularly with preterm newborns where it can cause blindness, lung and brain injury.

To address this need, PATH has developed a low-cost bCPAP kit which includes oxygen blenders that do not require electricity nor a source of pressurized air to blend oxygen with air. We seek to conduct an early feasibility study to:

1. assess the operational feasibility of using the PATH bCPAP kit including, when appropriate, in-line oxygen blending on neonatal patients and
2. assess the usability and acceptability of the PATH bCPAP kit with oxygen blenders by healthcare workers.

Newborns will be treated with the PATH bCPAP kit and a subset of these will also be treated with the PATH blender as needed to provide blended oxygen. Results from this study will be used to identify appropriate modification to the use procedures and/or the device as needed. Once testing is completed and product revision finalized, the PATH kit and blenders will allow resource-constrained settings to provide rigorously tested bCPAP therapy and blended oxygen to patients with reduced risk of morbidity from oxygen toxicity.

## 1.0 CHAPTER ONE: Introduction and Background

Preterm birth is responsible for 1/3 of paediatric deaths under age five.[2] Infants born very early suffer from respiratory distress syndrome due to under developed lungs and this is a leading cause of their deaths.[3] An additional 15% of children under age five die from trouble breathing due to respiratory tract infections such as pneumonia.[2] Continuous positive airway pressure (CPAP) provides constant distending pressure to the lungs and decreases the work of breathing for an infant. It is the recommended standard of care for respiratory failure caused by respiratory distress syndrome or pneumonia, and should be started as soon as the diagnosis is made.[4,5] The pressure provided by bubble CPAP (bCPAP) is regulated by the depth of the tube in the water bottle. The gas flow through the tube creates bubbling, and the resulting oscillations are helpful to a patient's lungs. Because of this, bCPAP is considered superior to standard CPAP in treating neonatal respiratory failure. Commercialized devices are available (Figure 1)[6], but are rarely found in resource constrained settings due to the prohibitive cost.

[figure not shown]

Figure 1. Commercialized bubble CPAP (bCPAP) circuit. These systems can cost up to 10,000USD. Figure from: [7]

Commercialized devices considered to be “low cost” do exist, however, at a price of US\$900, resource-constrained sites still cannot afford them or cannot afford enough devices for the number of patients requiring treatment.[8] To address this care gap, the World Health Organization (WHO) recommends creating improvised bubble CPAP (bCPAP) devices using components available in the hospital, specifically tubing connected to bottles, with water to generate the necessary pressure.[7] (Figure 2). These improvised kits, however, have variable performance in terms of pressure delivered due to the variation in the diameter and length of available tubing, lack of appropriate cannulae sizes, and incorrect assembly of parts.

[figure not shown]

Figure 2. Improved bCPAP created from a simple nasal cannula, as advised by the WHO. Although lifesaving, this system runs on 100% oxygen which can be toxic to patients. Figure from [7].

Additionally, most resource-constrained settings providing bCPAP therapy do not have a mechanism to provide blended gases (air and oxygen) to the baby. WHO guidelines strongly advise against the use of 100% oxygen with newborns—particularly preterm newborns—as it poses a risk for blindness, chronic lung disease and brain injury.[9,10] High resource

settings use a commercialized oxygen blender for this purpose. These blenders are not only expensive—about US\$1,000 each—but require that both oxygen and air are supplied from a pressurized source such as a wall supply or cylinders. Further, the pressure of both gases must be roughly equal in magnitude and at a pressure beyond the capability of most oxygen concentrators. Pressurized air is rarely available in resource-constrained settings as it has very few uses beyond mechanical ventilation. Therefore, the provision of blended oxygen is not available in most resource limited settings providing bCPAP.

## 2.0 CHAPTER TWO: Literature review

### **Neonatal mortality**

Over five million children under age five die annually worldwide - the majority in low resource settings.[11] The risk of death is highest in the first month of life, with 18 deaths per 1,000 live births globally, accounting for 2.5 million deaths overall.[11] Over the last 30 years, paediatric mortality has improved more quickly than neonatal mortality due to more rapid improvements in post-neonatal mortality.[12] Neonatal deaths are now responsible for nearly half (47%) of all childhood mortality. [11] Sub-Saharan Africa has the highest burden of paediatric mortality- 16 times the average mortality rate in high income countries. [11] In Uganda, neonatal mortality remains 28/1000 live births, and the largest cause of death is prematurity.[13] Accelerating implementation of available, cost-effective interventions for sick newborns is a factor into reducing this mortality.

### **Respiratory failure in neonates**

Respiratory failure is the final common pathway in the most frequent causes of neonatal death: preterm birth, infection, and birth asphyxia.[11] Preterm babies in particular have a deficiency in surfactant in their lungs and have difficulty keeping them open following birth. There is increasing attention on the care of the sick and small newborn including increased development of interventions for respiratory failure, such as bubble continuous positive airway pressure (CPAP).[14]

### **Evidence for bubble CPAP**

Bubble Continuous Positive Airway Pressure (bCPAP) is a simple, form of respiratory support that has been shown to decrease mortality in neonates with respiratory distress in both high and low resource settings.[15-17] Pressure delivery in bubble CPAP is due to the flow of air through a tube placed under water. The pressure is dependent on the depth of this tube. Bubbles emerging from the tube create oscillations which are transmitted to the patient's lungs. Treatment with bCPAP has been associated with improved clinical outcomes compared with other forms of CPAP.[18,19]

Bubble CPAP is increasingly used in low and middle income countries.[20-22] In Uganda it has been associated with improved mortality among preterm infants.[23,24] A 2020 publication from Mbale reported, among patients <1500 grams birthweight, the mortality rate decreased from 39% to 27% after the initiation of bCPAP (44% reduction in mortality, OR 0.56, 95%CI 0.36 – 0.86, p = 0.01).[23] The site of our study, Kiwoko Hospital, in Nakaseke district, was the site of bCPAP implementation in 2012 and one of the first published case series of such use in Uganda.[24]

### **Bubble CPAP Devices**

Bubble CPAP is strongly recommended for treatment of premature lung disease.[25] However there are limitations to available devices- commercialized bCPAP can cost over 10,000USD.[16] Lower cost commercialized bCPAP devices exist, however they cost 900 USD or more and low resource settings cannot afford enough units to serve the number of patients requiring bCPAP treatment.[26,27] The WHO recommends settings without access to commercialized devices create improvised bCPAP.[7] These improvised kits (Figure 2.) and

described in section one), use spare parts that are commonly available in facility settings and have allowed more settings to treat patients with bCPAP. Improvised kits have not been bench tested for reliability, and the design (using small bore oxygen tubing) varies considerably from those of commercialized designs. The need exists, therefore, for a low cost bCPAP design that has undergone testing to confirm it delivers accurate and appropriate pressure to a newborn.

### **Oxygen Safety**

Oxygen is life saving for newborns and is included in the WHO model list of essential medicines.[28] However the use of 100% oxygen can be dangerous. Excessive oxygen use causes retinopathy of prematurity (ROP), blindness or visual impairment in preterm infants. This is one of the leading causes of blindness around the world, causing 32,200 cases in 2010.[29] Currently ROP is most prevalent in middle income countries as neonatal care has scaled-up without safe oxygen management.[29] Oxygen-associated blindness is now being reported in Africa, likely associated both with increased oxygen use as well as ability to follow-up and detect this retinal damage in tertiary neonatal units.[30-32]

Although 100% oxygen should never be used for bCPAP therapy, many resource limited sites implementing bCPAP have access only to 100% oxygen.[9] Blending oxygen with room air allows it to be titrated to the patient's oxygen saturations and decreases the risk of hyperoxia. Low cost systems for delivering blended oxygen are required for safe bCPAP use.[9]

### 3.0 CHAPTER THREE: Statement of the problem, Justification and Conceptual framework

#### 3.1 Problem statement

The use of bCPAP devices can reduce mortality related to respiratory failure in newborns. However, devices operated with 100% oxygen increase the risk of morbidity in survivors, due to oxygen toxicity. There is a critical need for a safe, rigorously tested, very low-cost bCPAP kit including oxygen blender to be made available to resource-constrained sites.

#### 3.2 Justification of the problem

To address this need, PATH has developed a low-cost bCPAP kit which includes two fixed-ratio oxygen blenders (Figures 3 and 4) that do not require a source of pressurized air. These simple and inexpensive devices sit in-line from the oxygen source and dilute the flowing stream of oxygen with room air, obviating the need for a pressurized source of air. The oxygen may be supplied from either high-pressure sources or low-pressure sources such as oxygen concentrators. Each of the two blenders are single plastic parts, injection moulded from a biocompatible, medical-grade polyethylene resin. No electricity is required for the blenders to provide a stable and constant mix of air and oxygen over the full range of clinically relevant pressure and flows for newborns.

[figure not shown]
[figure not shown]

Figure 3. PATH BCPAP Kit with in-line blender (left) and close-up of oxygen blender (right)

## Oxygen Blender

**Figure 4. Mechanism of oxygen blender**

Two fixed ratio blenders are available: a ‘low’ blend that provides 37% oxygen, and a ‘high’ blend that provides 60% oxygen. The actual ratio of oxygen and air necessarily depends on the concentration of oxygen supplied to the blender but remains constant and stable for any given input.

Both the technological characteristics and intended use of PATH’s blenders are substantially equivalent to devices that are on the US market today. The mode of operation (air entrainment) has been employed by class 1 (low risk) oxygen diluter devices used for high-flow oxygen masks that have been commercially available since the 1970’s. Oxygen blenders (class 2, moderate risk) have been commercially available for a similar period, and provide variable blends of air and oxygen for respiratory support requiring some pressure—such as CPAP. The PATH fixed-ratio blenders combine the technological characteristics of the former (fixed-ratio air entrainment), with the intended use of the latter (CPAP therapy).

In the USA, the PATH blenders would be considered a class 2 device and would follow the substantial equivalence regulatory pathway, otherwise known as a 510(k) or premarket notification. Typically, class 2 devices are not required to demonstrate clinical safety or efficacy as their technological characteristics are well understood and their intended uses are identical to those of devices already cleared. Characterization of the device’s safety and performance can be demonstrated through performance testing of the flow, pressure and oxygen fraction. The verification test report for the bCPAP kit and blenders can be found in Appendix B.

We seek to conduct an early feasibility study (EFS), which is a limited clinical investigation of a device in development, typically before the device design has been finalized, for a specific indication (e.g., innovative device for an established intended use). The purpose of this study is to assess the operational feasibility, usability and acceptability of the device in a resource-constrained setting. Although there have been no prior studies in human populations with this device, oxygen blenders are a critical safety component of bCPAP therapy; providing unblended (100%) oxygen to premature infants can cause blindness, chronic lung disease, and brain damage. The World Health Organization recommends that blended oxygen or compressed air—not pure oxygen—be used for these patients.[7]

Once this study is completed, the device labelling and design may be revised if needed and prepared for manufacture by Sinapi biomedical (Stellenbosch, South Africa). This low-cost bCPAP kit with oxygen blenders will allow resource-constrained sites to provide rigorously tested bCPAP therapy and blended oxygen to patients with reduced risk of morbidity from oxygen toxicity. This study is aligned with WHO priorities. In 2018, the WHO called for more research to be done to explore simpler, cheaper technology to improve supportive care of newborns who require oxygen, including safe bCPAP therapy—estimating that the introduction of a low cost bCPAP kit with blenders in central and district hospitals would prevent 178,000 neonatal deaths in Africa each year.[27,33]

[figure not shown]
### 3.3 Study Product

#### Overview

The PATH bCPAP kit with oxygen blenders is intended to provide respiratory support to a neonate in respiratory distress where higher level means of respiratory support are not available. (See Appendix A for product label and instructions for use). This product is a single-use device for the purposes of this study. No changes to device design will be made during the study.

PATH's fixed-ratio, in-line oxygen blenders are small, single-use, injection moulded devices intended to provide a stable blend of air and oxygen to a neonate on bCPAP therapy. (Instructions for use in Appendix A). A blender is inserted (in-line) into the inspiratory limb of a bCPAP respiratory circuit and works by entraining room air into a stream of pressurized oxygen (based on the Bernoulli principle), producing a gently pressurized and blended gas that is delivered to the neonate (see Figures 4 and 5). The device provides a fixed ratio of air and oxygen that is consistent over the entire range of clinically relevant pressures (3 to 10 cmH2O) and remains consistent despite changes in flow (1 to 10 LPM). The blend is stable within  $\pm 5\%$  of the blender's nominal blend-ratio when used with 100% oxygen source, irrespective of the flow and pressure from the oxygen source, or the flow and pressure of the blended gas delivered to the neonate.

**Figure 5. Diagram showing the components of the PATH bCPAP circuit (tubing, cannula and bubbler) as well as placement of PATH oxygen blenders**

Flow and pressure of the blended gas are adjusted in the same manner as respiratory circuits containing no blender (i.e., by adjustment of the flow of gas entering the system and depth of the bubbler straw within the bCPAP bottle, respectively). To change the blend ratio, the blender is simply replaced with another to achieve a higher or lower percentage of oxygen delivered. Currently two fixed-ratio blenders have been developed; a “low blender” with a blend-ratio of 37% and a “high” blender with a blend-ratio of 60% (see Figure 6). The rationale for having two blends for this study is two-fold: (1) more blend ratios would complicate the decision-making process by the healthcare worker and (2) more blend ratios could increase the amount of time spent swapping out blenders. However, additional blend ratios between 37% and 60% can be produced if this study suggests that more blending options would be of benefit.

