**Table 1. Status of Fixed-Ratio Oxygen Blender Verification Tests**

Verification test	Criteria	Status
Blend stability*	Stable blend ( $\pm 5\%$ of nominal $FiO_2$ )	Passed
Temperature & humidity	Stable blend at 30 °C and 70% relative humidity	Passed
Noise	< 80 dBA	Passed
Shelf life†	Stable blend at 1 year	Pending
Biocompatibility	Per ISO 18562-2:2017	Passed

\*Blend stability testing has been conducted under worst case conditions of flow, pressure, temperature and humidity.

† Shelf life testing is based on accelerated aging test results at the time of writing and is intended to ensure performance of the device for the duration of the study. However, real-time shelf life testing is ongoing, and it is expected that the actual shelf life of the device will be confirmed to be much longer.

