### Oxygen Use

In the Kiwoko newborn care unit, oxygen concentrators are used for the delivery of oxygen. They are tested regularly for the amount of oxygen they provide, as older concentrators often provide a lower concentration of oxygen. During the study, oxygen concentrators will be tested weekly and labelled with the percentage of oxygen they produce.

Patients will receive continuous pulse oximetry monitoring while on bCPAP therapy in order to titrate oxygen according to the patient’s needs. However, oxygen saturations of sick infants can fluctuate frequently, making oxygen adjustments a challenge. There is a delicate balance between too little and too much supplemental oxygen exposure, as both can lead to harmful conditions, especially in premature infants. Consistent with WHO recommendations for oxygen use in neonates, the saturation goals are defined in the Table 5 below.(15) It is standard to set the alarm limits to 2% below and 2% above the target range.

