### 5.8.2 Data analysis

Table 13 presents a summary of variables, data sources and analysis plan. We will evaluate operational feasibility by analysing the domains below; each domain uses information from mixed data sources. We will create an index measure for each domain, all of which will be weighted equally. We will sum these index measures to determine overall operational feasibility.

- Ease of correct use: Median set-up time, frequency of correct set up, time to change blender, types and frequencies of user errors, frequency of changes to blend provided per day, frequency of bCPAP level adjustment per day
- Integration into service delivery: Count of patients treated with PATH bCPAP, Frequency of blending via air compressor and PATH blenders, Frequency of known bCPAP complications
- Confirmation of device functionality: Median and IQR of: FIO2 administered by PATH blenders (determined by blender used and FIO2 provided by concentrator), level of bCPAP (and min/max), total air/oxygen flow to bCPAP device (subset)
- Concentrator output: Ability to determine FIO2 delivered to patient
- Device malfunction: Frequency of device malfunctions with and without adverse events

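### The blender FiO2 listed as confirming device function is calculated from the blender label and a concentrator reading, so it cannot show whether the blender worked

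*Combined protocol and SAP*

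**What the plan says.** Section 5.8.2 (Data analysis) defines operational feasibility as the sum of equally weighted domain indices. One domain, "Confirmation of device functionality", reports the median and IQR of three items. The first is "FIO2 administered by PATH blenders (determined by blender used and FIO2 provided by concentrator"). The others are bCPAP level and, in a subset, total gas flow.

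Section 5.5 (Oxygen Use) says that the oxygen comes from concentrators, that "older concentrators often provide a lower concentration of oxygen", and that each concentrator will be tested and labelled weekly. The footnote to Table 8 says that the percentage delivered depends on the concentrator.

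On accuracy, section 3.3 (Overview) puts the blend within ±5% of the "nominal blend-ratio when used with 100% oxygen source, irrespective of the flow and pressure from the oxygen source". Section 3.2 adds that the ratio "remains constant and stable for any given input", without a tolerance. The footnote to Table 1 states: "Blend stability testing has been conducted under worst case conditions of flow, pressure, temperature and humidity". Source oxygen concentration is not among the conditions listed.

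The forms in section 5.7.2 and the data sources in Table 13 include a weekly concentrator output form and a patient form for bCPAP settings. None is described as recording oxygen after the blender.

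**The concern.** A measure that is meant to confirm function has to be able to come out differently when the device does not function. This FiO2 item takes the blender's ratio as given. If a blender entrains too little or too much air, both inputs (which blender was fitted, and what the concentrator last read) stay the same, and so do the reported median and IQR.

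The hypothesis in section 4.1 includes that patients will receive less than 100% oxygen, and the closing statement of section 3.3 gives the purpose as evaluating a reduction in oxygen delivered. An FiO2 computed from the label is below 100% whenever a blender is fitted, so it is not independent evidence of either. It also enters a feasibility score that may inform revision of the device before manufacture (section 3.2).

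**Working it through.** **Inputs from the documents.** Nominal blends N are 37% and 60% (3.3 Overview). Room air is 21% (3.3, text on adjustable blenders). The tolerance is ±5% of nominal with a 100% source. Concentrators are tested weekly.

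**Assumed.** The documents give no concentrator outputs. Source values S below 100% are illustrations over a range of 70% to 100%.

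**Step 1: the plan's own figures.** For a device that entrains room air at a fixed ratio, the source's share of the mixture is

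s = (N − 0.21)/0.79

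- 37% blender: 0.16/0.79 = 0.2025
- 60% blender: 0.39/0.79 = 0.4937

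and FiO2 = 0.21 + s × (S − 0.21). At S = 1.00 this returns 37% and 60% by construction. The ±5% is a bench result and cannot be re-derived from the text.

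**Step 2: source drift between weekly tests.** The change in true FiO2 is s times the change in source. For an unseen 10-point fall:

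- 37% blender: 10 × 0.2025 = 2.0 points
- 60% blender: 10 × 0.4937 = 4.9 points

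The calculated FiO2 does not move. If ±5% means 5% of nominal (1.85 and 3.0 points), both shifts exceed it. If it means 5 percentage points, neither does, although the second nearly reaches it. The plan does not say which meaning applies.

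**Step 3: blender fault.** Take an assumed 85% source. A working 37% blender gives 0.21 + 0.2025 × 0.64 = 34.0%. In the limiting case of no air entrained, it gives 85%. The plan would record the same number in both cases.

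**Step 4: does a lower source void the tolerance?** If the entrainment ratio does not depend on source concentration, a ±5-point tolerance at 100% scales by (S − 0.21)/0.79. At an 80% source this is 5 × 0.59/0.79 = ±3.7 points for either blender. The tolerance narrows and is not lost.

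**Step 5: the formula is not stated.** Section 5.8.2 names two inputs but not how they combine. Results for the 37% / 60% blender:

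| Assumed source | Mass balance | Label × source |
|---|---|---|
| 100% | 37.0 / 60.0 | 37.0 / 60.0 |
| 90% | 35.0 / 55.1 | 33.3 / 54.0 |
| 85% | 34.0 / 52.6 | 31.5 / 51.0 |
| 80% | 32.9 / 50.1 | 29.6 / 48.0 |
| 70% | 30.9 / 45.2 | 25.9 / 42.0 |

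At 85% the two rules differ by 2.5 and 1.6 points. Label × source ignores the oxygen in the entrained air, so mass balance is the rule that fits the mechanism in section 3.3.

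**Step 6: place in the score.** The domain is one of five with equal weight, and FiO2 is one of its three items. If items counted equally within the domain, which the plan does not say, FiO2 would carry 1/5 × 1/3 = 1/15 of the total.

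**The case against.** The strongest reply is that blender accuracy is not what this study tests. Section 3.3 treats safety and efficacy as settled at the bench and says that every blender was tested for oxygen fractionation before use. The objectives are feasibility, usability and acceptability. Device malfunction is a separate domain with its own count. This shows that the trial's main aims do not depend on the item. It does not rescue the item: pre-use testing does not show function in the field, and a malfunction count finds only faults that someone notices. If confirmation is not a purpose, the label is the thing to change.

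Three stronger readings are tempting, and the documents do not support them.

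- *That the study never uses a 100% source.* Section 5.5 says older concentrators often give less, but sections 5.2 and 5.5 also allow for patients receiving up to 100%. A 100% source is not assured; it is not excluded either.
- *That the plan relies on the 37% or 60% label alone, so that lower sources make its values wrong.* Section 5.8.2 uses the concentrator's output. The table's departures from nominal show how a correctly working blender depends on its source, and are not errors in the planned value.
- *That the whole domain is circular.* bCPAP level and gas flow do not depend on the blender's assumed ratio.

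Appendix B (verification report) and Appendix D (forms) are not in the published text. Bench data at lower source concentrations, or a field for measured FiO2, therefore cannot be ruled out.

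**Conclusion.** The concern holds for the FiO2 item only. As defined in section 5.8.2, that item restates the blender's design ratio applied to the latest concentrator reading, and it cannot reveal an off-ratio blender or drift between weekly tests. Drift moves true FiO2 by about 0.20 points (37% blender) or 0.49 points (60% blender) per point of source oxygen. The error from a blender fault cannot be bounded from the documents.

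The missing downstream measurement is the main ground. The 100%-source condition on the ±5% claim is secondary: accuracy at lower source concentrations is asserted without a figure, but a lower source does not by itself void the tolerance. The sizes rest on a fixed entrainment ratio, room air at 21%, and assumed source values. The effect on the summed score cannot be computed, because the plan does not say how a median and IQR become an index.

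**What to change.** In section 5.8.2, rename the item derived FiO2 and state the formula: FiO2 = 0.21 + (nominal − 0.21)/0.79 × (source − 0.21), with source taken from the most recent concentrator test. Report its median and IQR descriptively. Exclude this item, and not the whole domain, from the device-functionality index and the summed feasibility score. This costs a change of wording and one fewer item in the index.

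Alternatively, keep the item in the index and measure it. Read blended output from the blenders actually used, either in line or on the bench after removal, with the analyser that the weekly concentrator tests imply is on site (the text does not describe it). Record the source reading at the same time. Report the share of readings within ±5% of the value predicted for that source, and say whether ±5% means percentage points or a proportion of nominal. Because blenders are single-use, weekly readings on sample blenders would not test the units used on patients. With a target of 15 blender patients and one or both blenders used in each, this is roughly 15 to 30 readings.
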